# **3.2.** Secondary Endpoints

#### 3.2.1. Proportion of Patients with CR/PR and Steroid Dose 0.25 mg/kg or less

The proportion of patients with an acute GVHD response on Day 28 (CR or PR) and who are on a prednisone (or prednisone dose-equivalent corticosteroid) dose of 0.25mg/kg/day or less. Note

that use of prednisone below the threshold on the sirolimus arm will not be considered a failure for this endpoint.

# **3.2.2. Proportion of response**

Proportions of CR, PR, mixed response, no response and progression among surviving patients at Day 14, 28 and 56.

# **3.2.3.** Treatment Failure

Treatment failure is defined as: death, no response, progression, administration of additional therapy beyond primary therapy for GVHD ((or re-escalation of steroid dose to  $\geq$  2.5 mg/kg/day of prednisone (or methylprednisolone equivalent of 2 mg/kg/day) or initiation of corticosteroids for the treatment of acute GVHD for patients assigned to the sirolimus arm), at Day 14, 28, and 56.

# 3.2.4. Incidence of Chronic GVHD

Chronic GVHD is defined per NIH Consensus Criteria (see Appendix C). The incidence of chronic GVHD at 6 and 12 months post-randomization will be computed for each treatment arm, including organ involvement and severity, and overall global composite score (mild/moderate/severe).

# 3.2.5. Incidence of Systemic Infections

All microbiologically documented infections or significant infections requiring antibiotic/antifungal therapy occurring after initiation of therapy will be reported by site of disease, date of onset, and severity. For definitions see the BMT CTN MOP.

#### **3.2.6.** Event-Free Survival

Event-free survival is defined here as freedom from acute GVHD progression, chronic GVHD, malignancy relapse and mortality at 6 months and 12 months post-randomization.

#### Malignancy relapse is defined as follows:

Relapse is defined by either morphological or cytogenetic evidence of acute leukemia or MDS consistent with pre-transplant features, or radiologic evidence of lymphoma, documented or not by biopsy. Progression of disease applies to patients with lymphoproliferative diseases (lymphoma or chronic lymphocytic leukemia) not in remission prior to transplantation. The event is defined as increase in size of prior sites of disease or evidence of new sites of disease, documented or not by biopsy.

Acute leukemia and MDS – Relapse will be diagnosed when there is:

- Reappearance of leukemia blast cells in the peripheral blood; or,
- >5% blasts in the bone marrow, not attributable to another cause (e.g. bone marrow regeneration)
- The appearance of previous or new dysplastic changes (MDS specific) within the bone marrow with or without falling donor chimerism; or
- The development of extramedullary leukemia or leukemic cells in the cerebral spinal fluid or
- The reappearance of cytogenetic abnormalities present prior to transplantation

#### Lymphoproliferative Diseases – Relapse or progression will be diagnosed when there is:

- Appearance of any new lesion more than 1.5 cm in any axis during or at the end of therapy, even if other lesions are decreasing in size. Increased FDG uptake in a previously unaffected site will only be considered relapsed or progressive disease after confirmation with other modalities. In patients with no prior history of pulmonary lymphoma, new lung nodules identified by CT are mostly benign. Thus, a therapeutic decision should not be made solely on the basis of the PET without histologic confirmation.
- At least a 50% increase from nadir in the sum of the product diameters of any previously involved nodes, or in a single involved node, or the size of other lesions (e.g., splenic or hepatic nodules). To be considered progressive disease, a lymph node with a diameter of the short axis of less than 1.0 cm must increase by  $\geq$  50% and to a size of 1.5 x 1.5 cm or more than 1.5 cm in the long axis.

Lesions should be PET positive if observed in a typical FDG-avid lymphoma or the lesion was PET positive before therapy unless the lesion is too small to be detected with current PET systems (<1.5 cm in its long axis by CT).

- In addition to the criteria above, patients with CLL who present in complete remission prior to transplantation may fulfill the relapse definition if there is reappearance of circulating malignant cells that are phenotypically characteristic of CLL.

#### \*Institution of any therapy to treat persistent, progressive or relapsed malignancy, including the withdrawal of immunosuppressive therapy or donor lymphocyte infusion, will be considered evidence of relapse/progression regardless of whether the criteria described above were met.

#### 3.2.7. Disease-free and Overall Survival

Disease-free survival at 6 and 12 months post randomization. The events for disease-free survival are death and relapse of the underlying malignancy (see above – section 3.2.6 - definition for relapse/progression). Overall survival will be estimated at 6 and 12 months post-randomization.

# **3.2.8.** GVHD-Free Survival

GVHD-free survival will be estimated at 6 and 12 months post-randomization. Both acute and chronic GVHD will be considered in this estimate.

#### 3.2.9. Non-relapse Mortality

Non-relapse mortality at 6 and 12 months. The events for non-relapse mortality are death due to any cause other than relapse of the underlying malignancy.

# **3.3.** Exploratory Endpoints

#### 3.3.1. Steroid Dose

Doses of methylprednisolone will be converted to prednisone equivalents by multiplying the methylprednisolone dose by 1.25. The prednisone dose for each patient at Days 7, 14, 21, 28, 35, 42, 49, and 56 will be recorded. Prednisone doses for each patient will be converted to mg/kg. For patients that weigh over 100kg, maximal starting dose of prednisone will be 200mg (or 2mg/kg based on a modified starting weight of 100kg). For calculation of subsequent prednisone doses/kg on subsequent measures, the modified starting weight of 100kg will be used. The cumulative prednisone dose for each patient at Day 56 will be calculated by adding the doses (end of each week's dose) for each of the first eight weeks of treatment, divided by the number of days of survival during this interval.

#### **3.3.2.** Topical Therapy

The proportion of patients using either topical skin or topical GI steroids will be calculated as a secondary endpoint. Use of topical agents does not constitute systemic therapy, and does not result in designation of treatment failure.

#### 3.3.3. Discontinuation of Immune Suppression

The dates of discontinuation of corticosteroids and other systemic immune suppressive medications will be recorded. Incidence of discontinuation of immune suppression will be assessed at Days 56, 180, and 365 post-therapy. A composite endpoint of complete immune suppression discontinuation together with freedom from any GVHD or malignancy progression/recurrence will also be examined.

#### **3.3.4.** Incidence of EBV-associated lymphoproliferative disorder

Incidence of EBV-associated lymphoproliferative disorder and EBV reactivation requiring therapy, such as reduction or withdrawal of immunosuppression, Rituximab or chemotherapy.

#### 3.3.5. Steroid- and sirolimus- associated complications (collected in all patients):

# Incidence of hyperglycemia

Incidence of hyperglycemia (defined as a random glucose >200mg/dL or fasting glucose >126mg/dL) and use of diabetes therapy (use of insulin and/or oral medications to control and/or maintain glucose levels) at baseline, Day 28 and Day 56.

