#### **Duration of Steroids and Taper**

All patients should receive prednisone 2mg/kg/day PO (or methylprednisolone 1.6 mg/kg/day IV) for at least 3 full days (72 hours). This starting dose was carefully selected for the following reasons: (1) Both the clinical and biomarker-based risk stratification systems have been developed in the setting of patients treated with this starting prednisone dose; (2) The 2mg/kg/day starting dose was used in both BMT CTN 0302 and CTN 0802 trials, and expected prednisone response rates and allied power calculations for this trial are derived from this preliminary data; (3) Variable starting doses would confound the analysis of prednisone taper in this trial; (4) Prior randomized clinical trial data supported greater requirement for secondary systemic immune suppressive therapy in those treated with 1mg/kg vs. 2mg/kg starting dose. Thereafter (after 72 hours of 2mg/kg/day dose), the decision of when and how to taper is at the discretion of the treating physician. A potential prednisone taper is provided in Appendix E.

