#### Post-Randomization

The following post-randomization assessments are required of all patients, regardless of therapy received.

- 1. Karnofsky or Lansky performance status at Days 56, 90, 180 and 365
- 2. Complete acute GVHD staging and grading information including assessments of rash, diarrhea, nausea/vomiting, weight and liver function tests weekly through Day 56; Day 90, 6 and 12 months
- 3. Chronic GVHD evaluation (if present) Day 28, 56, 90, and 6 and 12 months
- 4. CBC with differential, chemistry (including liver function tests) weekly through Day 56; Day 90, 6, and 12 months
- 5. Fasting lipid profile at Day 28, 56, and 6 months
- 6. Toxicity evaluation weekly through Day 56; Day 90, 6 months and 12 months
- 7. Recording of all systemic immune suppression, including steroid dose and drug levels (as appropriate for sirolimus, cyclosporine, tacrolimus) weekly through Day 56, Day 90, 6, and 12 months. Second-line immune suppressive therapy (therapy beyond initial

randomized therapy of either sirolimus or prednisone) should be recorded at each of these time points.

- 8. Use of topical (skin, GI) steroid agents weekly through Day 56; Day 90, 6 and 12 months.
- 9. Data on systemic infections, and EBV PTLD (or EBV requiring therapy), recorded as per the BMT CTN (Technical) MOP through 12 months.
- 10. EBV & CMV monitoring as per institutional practice.
- 11. Myopathy assessments at Day 56 and 6 months.\*
  - a. Hip Flexor and Quadriceps Strength via handheld dynamometer
  - b. Two Minute Walk Test
  - c. 5-time Sit-to-Stand
  - d. Adult Myopathy Assessment Tool (AMAT)
- 12. Patient reported outcomes (M.D. Anderson Symptom Inventory, FACT-BMT, SF-36, or PedsQL (Pediatrics)) at Day 56, 6 months and 1 year.\* Only English speaking adult and pediatric patients, and Spanish speaking adult patients are eligible to participate in the Health Quality of Life (HQL) component of this trial. Patients >18 years will complete the FACT-BMT, MOS SF-36 and MDASI instruments. Patients ≥ 8 years through 18 years will complete the PedsQLTM Stem Cell Transplant Module.
- 13. OPTIONAL 30-40 mL blood samples for research laboratory studies at Day 7, 28, and 56 (see Appendix B).\* Patients with weight <13 kg will have ≤3 mL/kg collected at each individual time point.

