#### Table 4.4 – REQUIRED ASSESSMENTS

	Pre- Randomize	Pre- Pre- Days Post Randomization											
	Base	line	7*	14*	21*	28*	35*	42*	49*	56 *	90**	180***	365***
History and physical exam	Х												
Pregnancy test (if applicable)	Х												
Karnofsky/Lansky performance status		Х								Х	Х	Х	Х
Acute GVHD evaluation	Х		Х	Х	Х	Х	Х	Х	Х	Х	Х	Х	Х
Chronic GVHD evaluation						Х				Х	Х	Х	Х
CBC with differential, platelet count	Х		Х	Х	Х	Х	Х	Х	Х	Х	Х	Х	Х
Basic chemistry (creatinine)	Х		Х	Х	Х	Х	Х	Х	X-	Х	Х	Х	Х
Liver function tests (alkaline phosphatase, bilirubin, AST, ALT)	Х		Х	Х	Х	Х	Х	Х	Х	Х	Х	Х	Х
Fasting lipid profile		X 				Х				Х		Х	
Toxicity and AE evaluation		Х	Х	Х	Х	Х	Х	Х	Х	Х	Х	Х	Х
Recording of all systemic immune suppression, including steroid dose	Х		Х	Х	Х	Х	Х	Х	Х	Х	Х	Х	Х
Drug level monitoring (e.g. tacrolimus, cyclosporine)	Х	Х	Х	Х	Х	Х	Х	Х	Х	Х	Х	Х	Х
Use of second-line immune suppressive therapy			Х	Х	Х	Х	Х	Х	Х	Х	Х	Х	Х
Use of topical agents	Х		Х	Х	Х	Х	Х	Х	Х	Х	Х	Х	Х
Malignancy relapse, death			Х	Х	Х	Х	Х	Х	Х	Х	Х	Х	Х
Systemic infections	Х		Х	Х	Х	Х	Х	Х	Х	Х	Х	Х	Х
EBV PTLD, or EBV requiring therapy			Х	Х	Х	Х	Х	Х	Х	Х	Х	Х	Х
CMV reactivation requiring therapy			Х	Х	Х	Х	Х	Х	Х	Х			
Myopathy assessments		X 								Х		Х	
Patient-reported outcomes: MDASI, FACT-BMT, MOS SF-36, PedsQL 		Х								Х		Х	Х
REQUIRED 5 mL blood sample for Ann Arbor Panel Scoring collection	X 												
OPTIONAL Research blood samples for ancillary studies (see Appendix B) 		Х	Х			Х				Х			

\* +/- 3 days to allow for scheduling flexibility, holidays, etc. Subsequent visits through Day 56 must be scheduled weekly.

\*\* +/- 14 days to allow for scheduling flexibility

\*\*\* +/- 28 days to allow for scheduling flexibility

 The fasting lipid panel may be done up to 96 hours after enrollment.

 Myopathy assessments may be done up to 96 hours after enrollment.

 Only English speaking adult and pediatric patients, and Spanish speaking adult patients are eligible to participate in the Health Quality of Life (HQL) component of this trial. Patients >18 years will complete the FACT-BMT, MOS SF-36 and MDASI instruments. Patients > 8 years through 18 years will complete the PedsQLTM Stem Cell Transplant Module.

 Required blood sample for Ann Arbor Scoring must be collected prior to enrollment/randomization and shipped overnight immediately afterwards.

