#### 5. Incidence of hyperglycemia

Incidence of hyperglycemia and use of diabetes therapy at baseline, Day 28 and Day 56 will be estimated and compared between arms using a Z-test (or Barnard's Exact Unconditional as appropriate).

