# **APPENDIX E**

# SUGGESTED PREDNISONE TAPER FOR RESPONDING PATIENTS

### **APPENDIX E**

# SUGGESTED PREDNISONE TAPER FOR RESPONDING PATIENTS

Days Minimum of 3 days		Dose 2mg/kg/day	
Taper weekly thereafter at the	Week 2	0.5 mg/kg/day once daily	
following intervals	Week 3	0.25 mg/kg/day once daily	
	Week 4	0.2 mg/kg/day once daily	
	Week 5	0.1 mg/kg/day once daily	
	Week 6	0.1 mg/kg/day every other day	
	Week 7	Discontinue	

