#### **4.3.5 Hyperglycemia**

Hyperglycemia is defined as a random glucose >200mg/dL or fasting glucose >126mg/dL and use of diabetes therapy, i.e. use of insulin and/or oral medications to control and/or maintain glucose level. The incidence of hyperglycemia and use of diabetes therapy at baseline, Day 28, and Day 56 will be estimated and compared between arms using a Z-test for comparing binomial proportions (or Barnard's Exact Unconditional Test as appropriate).

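### Hyperglycemia and diabetes therapy are labelled incidence but read only at baseline, Day 28 and Day 56, so early events that resolve before Day 28 are not counted

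*Protocol*

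**What the plan says.** Protocol 3.3.5 takes hyperglycemia as a random glucose above 200 mg/dL or a fasting glucose above 126 mg/dL, and pairs it with "use of diabetes therapy (use of insulin and/or oral medications to control and/or maintain glucose levels) at baseline, Day 28 and Day 56". Protocol 5.2.6 (item 5) and SAP 4.3.5 keep those three days; the SAP says "The incidence of hyperglycemia and use of diabetes therapy at baseline, Day 28, and Day 56 will be estimated and compared between arms". Exhibit 1501-17 is a separate yes/no table for each day.

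On exposure:
- **Prednisone.** Protocol 2.5.4 requires 2 mg/kg/day for at least 72 hours, then leaves the taper to the treating physician. Appendix E, titled "SUGGESTED PREDNISONE TAPER FOR RESPONDING PATIENTS", lists 0.5 mg/kg/day in Week 2, 0.25 in Week 3, "0.2 mg/kg/day once daily" in Week 4, 0.1 in Week 5, 0.1 on alternate days in Week 6, and discontinuation in Week 7.
- **Sirolimus.** Protocol 2.5.3 asks for therapeutic sirolimus to at least Day 56. The target is 10-14 ng/mL until acute GVHD resolves and may then be lowered to 5-10 ng/mL. Table 1 lists hyperglycemia as common (over 20%) within 2-3 weeks.

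On data collection, Protocol 4.4 lists "CBC with differential, chemistry (including liver function tests) weekly through Day 56; Day 90, 6, and 12 months", while the matching row of Table 4.4 begins "Basic chemistry (creatinine" and names no other analyte in that row. Neither place names glucose or diabetes therapy on any day. Steroid dose is recorded weekly through Day 56 (Protocol 3.3.1).

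**The concern.** Sparing steroid toxicity is part of the case for the trial (Protocol 1.6), and Protocol 1.1 names hyperglycemia among the corticosteroid toxicities. The planned readings miss the weeks when steroid exposure is highest. A prednisone patient who needs insulin from Day 3 to Day 20 and then stops is scored as no event at both Day 28 and Day 56.

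No other planned output fills the gap. The toxicity table in Exhibit 1501-23 has no hyperglycemia row, and Supplemental Exhibits 1501-4 and 1501-5 summarise adverse events only by System Organ Class. If the planned comparison shows no difference, a reader cannot tell whether sirolimus spared no steroid hyperglycemia or whether the readings came too late to see it.

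**Working it through.** The documents give no expected rate, power or sample size for this endpoint, so there is no plan figure to reproduce. What can be checked is what the endpoint measures and where its reading days fall on the suggested taper.

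**1. Point prevalence or cumulative incidence?** The text reads status *at* three days, and one of them is baseline, where no on-study event can yet have occurred. The shell has one yes/no per day. Where the protocol means a cumulative measure it writes *by*: thrombotic microangiopathy by 6 months (3.3.5) and CMV therapy by Day 56 (3.3.6). The endpoint is therefore point prevalence.

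**2. Dose on the reading days** (Appendix E in calendar weeks, start 2 mg/kg/day).
- Day 28 is the last day of Week 4: 0.2 / 2 = 10% of the starting dose. If the Week 2 step begins on Day 4, Day 28 is on the 0.1 step: 0.1 / 2 = 5%.
- Across the visit window of ±3 days (Days 25-31) the dose is 0.1-0.2 mg/kg/day, or 5-10%.
- Day 56, and its window from Day 53, falls after the Week 7 stop: 0.

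**3. Share of the suggested dose already given.** Appendix E does not state the dose for Days 4-7, so three readings are used. Week 6 is taken as 0.05 mg/kg/day on average.
- A: Days 4-7 at 2. Weekly totals 14 + 3.5 + 1.75 + 1.4 + 0.7 + 0.35 = 21.7 mg/kg.
- B: Days 4-7 at 0.5. Week 1 = 3 × 2 + 4 × 0.5 = 8; total 15.7 mg/kg.
- C: Week 2 step starts on Day 4. 6 + 3.5 + 1.75 + 1.4 + 0.7 + 0.35 = 13.7 mg/kg.

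| Given by | A | B | C |
|---|---|---|---|
| Day 7 | 14 / 21.7 = 65% | 8 / 15.7 = 51% | 8 / 13.7 = 58% |
| Day 14 | 17.5 / 21.7 = 81% | 11.5 / 15.7 = 73% | 10.5 / 13.7 = 77% |
| Day 21 | 19.25 / 21.7 = 89% | 13.25 / 15.7 = 84% | 12.05 / 13.7 = 88% |
| Day 28 | 20.65 / 21.7 = 95% | 14.65 / 15.7 = 93% | 13.05 / 13.7 = 95% |

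Days 7, 14 and 21 are already study visits. On this taper they fall at 0.5-2, 0.25-0.5 and 0.2-0.25 mg/kg/day.

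**4. What a shrinking contrast would cost (assumed rates only).** Take 60 per arm, two-sided 5%, the normal approximation for two proportions, and an assumed 20% in the sirolimus arm. With p̄ the mean of the two rates, power = Φ{[|p1 − p2| − 1.96√(2p̄(1 − p̄)/60)] / √[(p1(1 − p1) + p2(1 − p2))/60]}. For prednisone rates of 50%, 40%, 30% and 25% this gives 94%, 67%, 24% and 10%. If a difference shrinks between the early weeks and Day 28, the planned test may well not detect it. These rates are illustrations, not estimates.

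**The case against.** The strongest case against has four parts.

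- **The taper need not be followed.** Appendix E is suggested, covers responders only, and gives way to physician discretion after 72 hours. Protocol 5.1.5 plans on 60% response and 30% in response at or below 0.25 mg/kg in the prednisone arm, so 30 / 60 = half of responders would still be above that dose at Day 28. In the earlier network trial it was 22.1% of patients at or below it, against 64.2% responding (22.1 / 64.2 = 34%), although the protocol warns that the 22.1% may be too low. This stands: the shares above describe Appendix E, not expected exposure. What survives is that the mandated 2 mg/kg/day period precedes Day 28 under any taper.
- **The contrast is not clean.** A reader might infer that Day 28 sets full-exposure sirolimus against nearly finished prednisone. The documents do not support that. The sirolimus target may drop once GVHD resolves, and sirolimus patients may start steroids: in the background series 16 of 32 did, at a median of 9 days (range 2-28; Protocol 1.5). They are analysed as randomized.
- **Glucose may already be collected.** The case report forms are described in a handbook outside these documents, and Table 4.4 omits glucose even on Days 28 and 56, where the endpoint needs it. Its silence about other weeks proves little. Still, no planned analysis uses a glucose value between baseline and Day 28.
- **Landmark days are a legitimate choice for an exploratory endpoint.** They validly estimate prevalence on those days, and no decision or stopping rule depends on them. This limits the weight of the point. It does not make the result an incidence.

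**Conclusion.** The point holds in a limited form. The plan measures prevalence on two on-study days under the name incidence, and the highest mandated prednisone exposure lies well before the first of them. Events that resolve before Day 28 are missed, so early hyperglycemia in the prednisone arm is likely to be understated. On Appendix E, 51-65% of the suggested dose is given by Day 7 and 93-95% by Day 28; slower tapers make the gap smaller by an amount the documents do not fix.

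A reader might go further and infer that the result is biased against sirolimus, or could reverse. That is plausible but not shown. The documents give no hyperglycemia rates, share of dose is not a rate of events, sirolimus is itself listed as a common cause within 2-3 weeks (so early sirolimus events can be missed too), and later steroid starts blur the sirolimus arm. The primary result is unaffected. The change is worth making because it is cheap and concerns a toxicity that the trial hopes to reduce.

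**What to change.** - **Collect.** At baseline and at the existing weekly visits from Day 7 to Day 56, record glucose (marked fasting or random) and current diabetes therapy in both arms, using the chemistry already drawn. Name both items in Protocol 4.4 and Table 4.4.
- **Analyse.** Define two separate endpoints: any hyperglycemia, and any new diabetes therapy, each through Day 28 and through Day 56, compared with the planned Z test or Barnard's test. Keeping them apart also settles SAP 4.3.5, whose definition can be read as requiring both a raised glucose and treatment.
- **State the denominators.** Limit each endpoint to patients without that condition at baseline, and describe the baseline-positive patients separately. Keep patients who die early in the denominator, classified by the events observed before death.
- **Keep** the Day 28 and Day 56 readings as descriptive prevalence.

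The cost is one laboratory value with its fasting status and one yes/no field per weekly visit, plus revised wording in Protocol 3.3.5 and 5.2.6, SAP 4.3.5 and Exhibit 1501-17. No visit, sample or treatment changes, assuming glucose can be reported from the weekly chemistry; the documents do not confirm that.

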# **Functional Myopathy**

Change from baseline in functional myopathy score at Day 56 and 6-months post-randomization.

- i. Hip Flexor and Quadriceps Strength via handheld dynamometer
- ii. Two Minute Walk Test
- iii. 5-time Sit-to-Stand
- iv. Adult Myopathy Assessment Tool (AMAT)

# Hyperlipidemia

Incidence of hyperlipidemia as measured by fasting lipid panel at baseline, Days 28, 56 and 180 post-randomization. The proportion of patients in each study arm with elevation outside of normal range for each of the measured components of the fasting lipid panel (e.g. total cholesterol, LDL, HDL, and triglycerides) will be compared. Lipid parameters and use of lipid-lowering medications will be collected.

